5.3.1. Analysis of Objective Response Rate

The objective response rate and its 95% CI based on the Clopper-Pearson method will be provided. The proportion and 95% CI of participants with CR, PR, Stable Disease (SD), Progressive disease (PD) and Not Evaluable (NE) as defined by RECIST v1.1 will also be summarized and listed by visit.

Tumor size, defined as the sum of the target lesion diameters per RECIST v1.1, will be summarized as percent change from baseline by visit. In addition, the percent change from baseline in the sum of target lesion diameters as identified by RECIST v1.1 by the best overall response will be displayed graphically using a waterfall plot.

5.3.2. Sensitivity Analyses of Objective Response Rate

There is no sensitivity analysis of objective response rate. Post hoc analyses may be performed if deemed necessary.

5.3.3. Subgroup Analysis for Objective Response Rate

See Section 4.6 for subgroup analysis.

5.4. Secondary Efficacy Endpoints

Analysis of secondary endpoints will be conducted using the Full Analysis Set.

5.4.1. PFS-6

PFS-6 will be estimated using Kaplan-Meier method and 2-sided 95% CI based on log-log transformation. Participants who do not progress or die will be censored according to the censoring rules for the PFS as outlined in Table 3.

5.4.2. OS-2

The Kaplan-Meier method will be used to estimate the OS-2. Death due to any reasons will be an event. Participants who did not die at 2 years will be censored.

5.4.3. Change from Baseline in FOSI-8

Functional Assessment of Cancer Therapy (FACT) Ovarian Symptom Index-8 item version (FOSI-8) was used in this study for description of each item in FOSI-8 version 4, see Section 8.2.

Participants are asked to circle or make one number per statement to indicate their response as it applies to the past 7 days. In each statement, the numbers and meaning are as follows: 0 = Not at all, 1 = A little bit, 2 = Somewhat, 3 = Quite a bit, 4 = Very much. Except for statement 7 (I am content with the quality of my life right now), a lower number in the answer indicates a better condition. The response to the statements except for the statement 7 will be reversed and the sum of non-missing responses will be calculated.

The total FOSI-8 score will be summarized as sum of (8 question items) x 8 divided by the number of items answered. The FOSI-8 total score will range from 0 to 32 and a higher score is good. Therefore, a score of “0” is a severely symptomatic participant and the highest possible score is an asymptomatic participant. The FOSI-8 total score will be set to missing if 5 or more of the 8 item responses are missing.

Summary statistics of change from baseline in the FOSI-8 total score and the individual item responses will be summarized for each visit. In addition, the proportion of participants who achieved ≥ 2 improvement in FOSI-8 total score from baseline ([Beaumont et al. 2007](#)) will be summarized by each visit. Participants who could not possibly improve by at least 2 points due to a high score at baseline will be excluded from this analysis. A box and whisker plot displaying the total score over time by nominal visit and a figure for median change from baseline overtime will also be provided.

To evaluate association between changes of tumor size over time and the FOSI-8 total score, a figure with the percent change from baseline in tumor size on one y-axis and the change from baseline in FOSI-8 total score on a secondary y-axis over time (x-axis) will be generated.

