1.3. Study Design

This is a multi-center, single-arm, Phase 2 open label treatment study to determine the efficacy, safety, tolerability, and pharmacokinetics of nirogacestat in adult participants with recurrent OvGCT. Participants must have received at least one prior course of systemic therapy for OvGCT and have measurable disease by RECIST v1.1 to meet the eligibility criteria.

The Schedule of Assessments (SoA) is in protocol Section 1.3, Table 2. Participants will be screened up to 28 days prior to the first dose of study treatment (nirogacestat) and full eligibility will be based on the inclusion and exclusion criteria (Protocol Section 7.1 and 7.2).

Participants will administer 150 mg (3 × 50 mg tablets) of study treatment BID, continuously in 28-day cycles. Participants will remain on study treatment until death, disease progression (unless the participants meet criteria for continued treatment), discontinuation of study treatment for any reason, the study is stopped by the Sponsor for any reason, or participant qualifies for Sponsor's Compassionate Use Program.

All scans will be performed and read locally by the site's radiologist for Tumor assessment as per RECIST v1.1. Same modality used at Screening must be used at each subsequent imaging visits. Baseline scan is defined as scans performed prior to first dose of study treatment. On treatment scans are performed every 8 weeks (C3D1, C5D1, C7D1) for the first 6 months and then every 12 weeks (C10D1, C13D1, etc.) thereafter. Scans may be performed (-) 7 days prior to the visit.

The final 2-year survival check-in will occur approximately 2 years after the first dose of study treatment. If participant discontinues from study treatment prior to the 2-year check-in, quarterly telephone or email contact following EOT is required until the 2-year survival data point has

been collected. In addition, collection of subsequent anticancer therapy after nirogacestat and overall response to this therapy will be recorded. Only information about the subsequent therapy used directly after nirogacestat is required along with the final survival outcome at the 2-year check point.

Participants who discontinue study treatment early for any reason should return to the clinic for an End of Treatment (EOT) visit within 7 days after the Investigator determines study treatment will no longer be used and then again for a safety Follow-up (FUP) visit 30 days (+7 days) after the last dose of study treatment.

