1.4. Sample Size Determination

A prior GOG phase 2 trial in previously treated participants with stromal tumors evaluated the efficacy and safety of bevacizumab monotherapy in participants with recurrent sex cord stromal tumors of the ovary. The ORR in this study was 16.7% ([Brown et al. 2014](#)). Following this outcome, the ALIENOR/ENGOT ov7 trial randomized participants to see if the addition of bevacizumab to paclitaxel had effect on the PFS rate among participants with relapsed ovarian sex cord stromal tumors. While the combination therapy of paclitaxel and bevacizumab showed an ORR of 44% over paclitaxel monotherapy, the PFS remained equivocal between the two treatment groups ([Ray-Coquard et al. 2020](#)). Based on the ORR from the bevacizumab monotherapy trial, this study aims for an ORR of 30% with PFS as a secondary endpoint.

Since this is a first-in-human proof of concept study for the indication, no formal hypothesis testing or sample size calculation is contemplated. The initial goal of accrual for this study is 43 participants which should provide sufficient sample size for interim evaluations for futility with a Bayesian strategy of continuous monitoring. Participant accrual will not be paused during the interim evaluations. The Bayesian approach to be used for futility analysis assumes a

beta-binomial distribution with an uninformative prior of beta distribution ([Lee and Liu 2008](#); [Chen et al. 2019](#)). Assume at an assessment point, the study has accrued X responders out of n (≤ 43) participants. With a prior distribution of *beta* (a, b), X follows a binomial distribution and the posterior distribution of the response rate follows a beta distribution with parameters $(a+x, b+n-x)$, where x is the observed value of X . Thus, the number of responses in the potential $(43-n)$ future participants, Y , follows a beta-binomial distribution with parameters $(43-n, a+x, b+n-x)$. From the observed responders x and a target ORR, the predictive probability of reaching the target ORR at the end of study can be calculated with the beta-binomial distribution. If the predictive probability is too low, e.g., $\leq 10\%$, the study may be terminated for futility. A high predictive probability, e.g., $>85\%$, suggests high likelihood of achieving treatment efficacy at the end of the study.

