4.8. Missing Data Conventions for Efficacy Endpoints

There will be no imputation or substitutions made to accommodate missing efficacy data points. All data recorded on the eCRF will be included in data listings that will accompany the CSR.

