5.5.2. Next Generation Sequencing status

The NGS status will be assessed at baseline to detect FOXL2 C134W mutation as well as other genomic alterations and correlate these with response. A 2×2 table will be generated for FOXL2 C134W mutation (yes/no) vs. Objective Response (yes/no) to evaluate the correlation between mutation and ORR with the Spearman rank correlation and its 95% CI provided. Within each status, the percentage of participants with objective response (CR + PR) and its 2-sided exact 95% CI based on the Clopper-Pearson method will be provided. The response ratio of participants with alteration vs. those without alteration and its 95% CI will also be provided using the Farrington-Manning method.

NGS status data will be listed. Correlation between ORR and other genomic alterations will be analyzed post hoc if deemed necessary.

5.5.3. Inhibin A&B, Follicle-stimulating Hormone, Estradiol, CA-125, and AMH/Mullerian Inhibiting Substance (MIS)

Tumor and hormonal markers Inhibin A, Inhibin B, AMH/MIS, follicle-stimulating hormone, estradiol, and CA-125 will be assessed per the SoA (see Table 2 in the protocol). Summary statistics and change from baseline at each visit will be provided. Box and whisker plots displaying the values over time by nominal visit will also be provided.

To evaluate association between changes in tumor size over time with FSH and estradiol level, a figure with the percent change from baseline in tumor size on one y-axis and the change from baseline in FSH and estradiol level on a secondary y-axis over time (x-axis) will be generated.

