6. CHANGES TO PLANNED ANALYSES

Notable changes from the protocol-defined statistical analyses compared to this statistical analysis plan are described below:

- I. PFS-6 was redefined as a survival probability.
- II. Definitions and analysis method were added for PFS and OS.
- III. The planned informal interim analysis using the Bayesian approach for early futility stopping based on ORR was not performed. Due to this study's rapid enrollment, it was not feasible to perform the planned informal interim analysis using the Bayesian approach because, instead of 10 participants, 53 were enrolled before the one year predicted cutoff time point.
- IV. Additional preferred terms were added in electrolyte abnormalities – protocol Section 4.3 vs. SAP section 8.4.1.4.

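### The SAP says it evaluates how tumor-size change relates to FOSI-8, FSH and estradiol, but plans only a dual-axis plot over time, which gives no participant-level measure of association

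*SAP*

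**What the plan says.** SAP 5.4.3 (Change from Baseline in FOSI-8) gives this aim and method: "To evaluate association between changes of tumor size over time and the FOSI-8 total score, a figure with the percent change from baseline". Tumor size takes the first axis. For the other axis, the section says that "the change from baseline in FOSI-8 total score on a secondary y-axis over time (x-axis) will be generated".

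SAP 5.5.3 (tumor and hormonal markers) uses the same device: "To evaluate association between changes in tumor size over time with FSH and estradiol level, a figure with the percent change from baseline". There the second axis carries FSH and estradiol change.

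Neither section names a coefficient, a model, a confidence interval or a plot of paired values. Neither says whether the curves are means, medians or individual participants. SAP 8.3 places the figure shells in separate documents.

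The SAP does specify an association measure elsewhere. For FOXL2 mutation against response, SAP 5.5.2 will "evaluate the correlation between mutation and ORR with the Spearman rank correlation and its 95% CI provided".

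On missing values, SAP 4.8 says: "There will be no imputation or substitutions made to accommodate missing efficacy data points".

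**The concern.** Association here means that participants whose tumors shrink more also report better symptoms or show different hormone levels. That can be judged only from values paired within participants. Two series plotted against time are never paired, and how closely they appear to match depends on how the two axes are scaled.

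With visit-level means or medians there is a further problem. Two averages can drift together because both change with time on treatment, or because participants doing badly on either measure leave. Neither requires any relation between one participant's tumor change and the same participant's FOSI-8 change. Conversely, if both averages stay flat, a real between-participant relation does not show.

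This is the only planned link in the SAP between tumor change and the secondary symptom endpoint. In an open-label single-arm trial, a reader could take two mirrored curves as evidence that shrinkage brings relief.

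**Working it through.** The plan gives no numerical figure for this association, so there is nothing to reproduce. The check asks what two mean curves would show when the truth is known.

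**Inputs from the documents**
- Sample size: "The initial goal of accrual for this study is 43 participants"; SAP section 6 reports that "53 were enrolled before the one year predicted cutoff time point". Both 43 and 53 were used.
- Scan times: "On treatment scans are performed every 8 weeks (C3D1, C5D1, C7D1) for the first 6 months", then every 12 weeks (C10D1, C13D1). That gives five post-baseline scans in year one, after 8, 16, 24, 36 and 48 weeks of treatment.

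The slopes, SDs and dropout rules below are assumptions. The documents give none of them.

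**Check A: dropout and trend (3,000 trials per setting, N = 53)**

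Tumor change = bᵢ·t + noise, with bᵢ ~ N(0, SD 1.2 percentage points/week) and noise SD 5. FOSI-8 change = cᵢ·t + noise, with cᵢ ~ N(μ, SD 0.08 points/week) and noise SD 2. bᵢ and cᵢ are independent, so the true association is zero. Progression dropout means exit at tumor change of +20% or more. Symptom dropout means exit at a FOSI-8 change of -5 or worse. The statistic is the correlation r of the five pairs of visit means.

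| Setting | Trials with r < -0.8 |
|---|---|
| No dropout, μ = 0 | about 10% |
| Progression dropout only, μ = 0 | 15% |
| Both dropout rules, μ = 0 | 37-39% over repeated runs (median r about -0.7) |
| Both dropout rules, μ = 0.03/week | 80-82% over repeated runs |

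With N = 43 the last three rows become 15%, 34% and 75%. In the same null data, the same-visit participant-level Spearman coefficient averaged 0.00 and was nominally significant in 4-5% of trials.

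**Check B: drift without dropout (4,000 trials per setting)**

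Scans at months 2, 4, 6, 9 and 12. Between-participant slope SDs are 2.5 percentage points/month (tumor) and 0.4 points/month (FOSI-8); residual SDs are 8 and 2.5. The threshold here is two-sided.

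| Mean drift per month (tumor, FOSI-8) | True slope correlation | Median r of mean curves, N = 43 / 53 | Trials with \|r\| > 0.8, N = 43 / 53 |
|---|---|---|---|
| -2, +0.25 | 0 | -0.95 / -0.96 | 94% / 96% |
| -1, +0.15 | 0 | -0.85 / -0.88 | 60% / 68% |
| 0, 0 | 0 | about 0 | 16% / 15% |
| 0, 0 | -0.6 | -0.25 / -0.24 | 17% / 16% |

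In the three null rows, the month-6 Spearman coefficient averages 0.00, with p < 0.05 in about 5%. In the last row a real association exists, yet strongly correlated curves are no more frequent than under the null. The participant-level Spearman averages -0.35 there and is detected in 65% (N = 43) or 73% (N = 53).

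**Precision of the Spearman coefficient**

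95% limits = tanh[atanh(r) ± 1.96·√((1 + r²/2)/(N - 3))].
- r = 0, N = 53: 1.96/√50 = 0.277, so ±0.27.
- r = 0, N = 43: 1.96/√40 = 0.310, so ±0.30.
- r = 0, 30 pairs: ±0.36; 20 pairs: ±0.44.
- r = -0.5, N = 53: 0.549 ± 1.96·√(1.125/50) = 0.549 ± 0.294, so -0.69 to -0.25.

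**The case against.** **The figure has not been seen.** The artefact needs group curves, and the SAP does not say that group curves are planned. Individual panels would show co-movement within a participant, though still without a measure. This stands, and it limits the second half of the point to means or medians.

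**The larger dropout result needs an assumed exit rule.** A reader might infer that progression dropout, with no imputation, is enough to make the curves mirror each other. It is not: progression dropout alone gives 15%, against about 10% with no dropout. Protocol section 9 lets clinically stable participants continue past progression, and FOSI-8 is also collected at end of treatment and safety follow-up. Symptom-driven exit is possible under section 9, which lists clinical progression and physician judgement, but no rule is tied to a FOSI-8 fall. This stands.

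**Correlating five means ignores scale.** With both dropout rules and no trend, mean FOSI-8 moves only about 0.69 points from week 8 to week 48 on a 0-32 scale, below the 2-point improvement SAP 5.4.3 counts. How marked that looks depends on axis limits that are not given. This stands for that setting.

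**FSH and estradiol were not simulated,** and symptom-driven dropout does not carry over to them. Common drift might: protocol 4.1 reports raised FSH in women given nirogacestat in desmoid trials. SAP 8.4.1 notes that most participants here have had ovaries or uterus removed or are post-menopausal, so the extent is unknown. The lack of any association measure applies to these figures regardless.

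**Little depends on it.** The tumor-symptom association is not a listed objective, and SAP 4.5 contemplates no formal testing. A descriptive figure is a normal choice. This is why the point is minor; it does not answer the mismatch between the stated aim and the method.

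**Conclusion.** The mismatch is firm on the text. SAP 5.4.3 and 5.5.3 set out to evaluate an association and plan a display that yields no participant-level measure of one.

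That the display can mislead is conditional on group curves. Its size then runs from near chance (about 10-15% of null trials below -0.8, with no trend and no symptom-driven dropout), through about 37% with symptom-driven dropout, to about 80% with a small common FOSI trend as well. With drift in both means and no dropout, 60-96% of null trials exceed 0.8 in absolute value. These figures rest on assumed slopes, SDs and exit rules. The direction of the problem does not depend on those choices; the percentages do.

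Two stronger readings are not supported. A reader might infer that the figure will show a false link between shrinkage and relief; the documents establish neither what is plotted nor the dropout or drift that would be needed. A reader might also infer that the symptom endpoint or the response analysis is compromised. ORR, PFS-6, OS-2, DoR and the FOSI-8 change summaries are untouched. This is an improvement worth making, not a defect in the trial's main conclusions.

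**What to change.** - In SAP 5.4.3 and 5.5.3, describe the dual-axis figure as a descriptive display. State whether it shows means, medians or individuals, and print n per visit for each curve.
- Add a same-visit scatter plot of percent change in tumor size against change in FOSI-8, with a Spearman coefficient and 95% CI, at one named scan visit such as C7D1. Do the same for FSH and estradiol. Label all three exploratory and report the number of pairs.
- Do not add a repeated-measures correlation over all visits unless it adjusts for visit. Unadjusted, it keeps common time trends. In null simulations it was nominally significant in 14% (both dropout rules, no trend), 32% (with the 0.03/week FOSI trend) and about half of trials (drift in both means, no dropout).
- Do not compare FOSI-8 change by confirmed-responder status unless a landmark is set, because a participant must stay on study long enough to be confirmed as a responder.

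The cost is a few extra outputs from data already collected, using a type of measure the SAP already specifies for FOXL2. The estimate will be imprecise: about ±0.27 at r = 0 with 53 pairs, and ±0.44 with 20.

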5.4.4. Duration of Response (DoR)

DoR will be summarized with standard summary statistics and will also be analyzed using the Kaplan-Meier method for confirmed responders only. Quartiles (i.e., the 25th, 50th, and 75th percentile estimates) and the 2-sided 95% confidence intervals will be presented. If progression

or death was not observed, the participant will be censored according to the censoring rule for PFS (see Table 3). If there are censored participants in DoR, time to censoring will be used to summarize the range. The Kaplan-Meier plot will be provided.

By-participant listing will be provided for responders. The listing will include number of completed cycles before first response, date of first response, date of first disease progression or death if any, censored or event will be marked.

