**Table 13: Statistical Method for Efficacy Analyses**

Primary Endpoint	Statistical analysis methods
Objective response rate, defined as the proportion of participants with CR + PR using RECIST v1.1	The response rate will be calculated, and the exact 95% CI will be provided. The proportion and 95% CI of participants with CR, PR, Stable Disease (SD), and Progressive disease (PD) will also be summarized and listed by visit.
Secondary Endpoint	Statistical analysis methods
Estimate of proportion of participants who have not progressed or died at 6 months of follow-up: PFS-6. Progression is defined by RECIST v1.1	The Kaplan-Meier (K-M) method will be used to estimate PFS-6.
Estimate the 2-year overall survival, defined as the proportion of participants who have not died after 2 years of follow-up after their first dose of nirogacestat	The K-M method will be used to estimate the distribution of overall survival
Change from baseline in FOSI	Change from baseline in the FOSI score and the individual responses will be summarized at each cycle, end of treatment, and the follow-up visit.
DoR, defined as the time from first assessment of response (CR + PR using RECIST v1.1) to first disease progression defined by RECIST v1.1 or death, whichever comes first	The K-M method will be used to estimate the distribution of the duration of response including median.
Exploratory Endpoint	Statistical analysis methods
Exploratory endpoint statistical analysis method will be described in the SAP.	

CI = Confidence interval; CR = Complete response; FOSI = Functional Assessment of Cancer Therapy – Ovarian Symptom Index; K-M = Kaplan-Meier; ORR = Objective Response Rate; PFS = Progression-Free Survival; PR = Partial Response; RECIST v1.1 = Response Evaluation Criteria In Solid Tumors version 1.1; SAP = Statistical Analysis Plan

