4. STATISTICAL METHODOLOGY

4.1. General Information

All data listings that contain an evaluation date will have a relative study day associated with treatment start (Rel Day). Pre-treatment and on-treatment study days represented as Relative Day are numbered relative to the day of the first dose of study medication which is designated as Day 1. The preceding day is Day -1, the day before that is Day -2, etc.

Tabulations will be produced for appropriate disposition, demographic, baseline characteristics, efficacy, and safety parameters. For categorical variables, summary tabulations of the number and percentage of participants within each category (with a category for missing data) of the parameter will be presented. For continuous variables, the number of participants, mean, median, standard deviation, minimum, and maximum values will be presented. Time-to-event data will be summarized using 25th, 50th (median) and 75th percentiles and time point survival probabilities (at 6 months, 1 year, 18 months, 2 years, etc.) with associated 2-sided 95% confidence intervals (CIs) using Kaplan-Meier methodology and the log-log transformation, as well as number and percentage of events and censored observations.

Graphical displays will be provided where useful to aid in the interpretation of results. A swimmer plot may be used to present the exposure to study treatment, overall response and follow up for all participants in the Full Analysis Set. Each participant will be presented on a horizontal bar (y-axis) over time (x-axis) starting at treatment start date. For each participant's bar, the plot will include best overall response (CR, PR, SD, PD, or NE), end of response or continued response (at censored timepoint).

The following conversion conventions will be applied:

- CIs will be presented to 1 more decimal place than the raw data
- Weeks will be calculated as number of days divided by 7
- Months will be calculated as number of days divided by 30.4375
- Years will be calculated as number of days divided by 365.25
- Cycles as used in adverse event summaries are defined as every 28 days
- Day 1 will be considered as the first day of treatment

All tables, figures, and listings will include footers at the bottom of the page reflecting the path of the programs used to generate the tables, figures, and listings, and date and time of the generation of the output.

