5.5.4. Time to Response

Time to first objective response will be calculated as time in months from first dose until date of the first documented response (CR or PR). Only participants with confirmed response will be included and the time in months to first response will be summarized with standard summary statistics.

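### SAP 5.4.4 adds ordinary summary statistics for duration of response, a censored endpoint, beside Kaplan-Meier; a mean would be biased low, and the median may be.

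*SAP*

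**What the plan says.** SAP 5.4.4 plans two things for DoR, in confirmed responders: "DoR will be summarized with standard summary statistics and will also be analyzed using the Kaplan-Meier method". It goes on: "Quartiles (i.e., the 25th, 50th, and 75th percentile estimates) and the 2-sided 95% confidence intervals will be presented". Responders without progression or death are censored by the PFS rules in SAP Table 3, whose title covers DoR. On censored values in the descriptive summary there is one sentence: "If there are censored participants in DoR, time to censoring will be used to summarize the range". A Kaplan-Meier plot and a by-responder listing that marks event or censored are also planned.

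SAP 4.1 has two default rules. For ordinary measurements: "For continuous variables, the number of participants, mean, median, standard deviation, minimum, and maximum values will be presented". For time-to-event data: "Time-to-event data will be summarized using 25th, 50th (median) and 75th percentiles and time point survival probabilities", by Kaplan-Meier, with counts of events and censored observations and no mean or SD.

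SAP 5.5.4 uses the same phrase as 5.4.4 for time to response in confirmed responders, where nobody is censored: "the time in months to first response will be summarized with standard summary statistics".

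Protocol Table 13 gives one method for DoR: "The K-M method will be used to estimate the distribution of the duration of response including median". SAP Section 6, which lists the notable departures from the protocol's analyses, does not mention the added summary. SAP 4.8 rules out imputing or substituting missing efficacy data.

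**The concern.** A responder still in response at the last adequate scan has a DoR known only to exceed the observed time. An ordinary mean or SD of such data needs a rule for these responders, and the SAP gives none. With imputation excluded, two simple routes remain: use the censoring time as if the response had ended then, or leave ongoing responders out. Both shorten the reported duration, and more so the longer responses last.

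DoR is the secondary endpoint that shows what the response rate is worth. If the added summary is produced, the report may carry a mean DoR, and possibly a second median, that disagrees with the Kaplan-Meier result beside it. In a single-arm trial of a slow-growing tumor, where ongoing responses at analysis are plausible, that figure would understate the treatment and could be quoted without its qualification.

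**Working it through.** **Step 1: which reading is natural?** In 5.4.4 the word *also* separates the first summary from Kaplan-Meier. The same phrase in 5.5.4 describes an uncensored continuous variable. The list in SAP 4.1 for such variables is n, mean, median, SD, minimum and maximum. The other time-to-event endpoints, in SAP 5.5.1 (PFS, PFS on continued treatment, PFS2, OS), get Kaplan-Meier without this extra summary. So the continuous-variable list is the likelier meaning, although 5.4.4 does not spell it out.

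**Step 2: inputs.** The documents give no assumed DoR, so there is no planned figure to reproduce.

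- Responders: 30% target ORR (SAP 1.4) × 43 = 12.9, about 13; × 53 enrolled (SAP 5.8) = 15.9, about 16.
- Assumptions not in the documents: exponential DoR with true median 6, 12, 18 or 24 months; response about 2 months after first dose; uniform independent censoring.
- Early case: 6-18 months of follow-up from first dose, so censoring 4-16 months after response. This stands for a readout near the ORR analysis, which Protocol 6.1 times at the last participant's C7D1 scan, or for scans that end with treatment.
- Mature case: 24-36 months of follow-up, so censoring at 22-34 months. This follows the minimum of 2 years' follow-up and the estimated 3-year duration (SAP 1.3), if tumor assessment lasts that long.

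**Step 3: direct calculation, true median 12.** True mean θ = 12/ln 2 = 17.3. With censoring uniform on (a, b), the expected share censored is p = [θ/(b−a)] × (2^(−a/12) − 2^(−b/12)). The mean with censoring times taken as complete is θ(1 − p).

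- Early: p = 1.4427 × (0.7937 − 0.3969) = 0.57; mean = 17.31 × (1 − 0.5725) = 7.4.
- Mature: p = 1.4427 × (0.2806 − 0.1403) = 0.20; mean = 17.31 × (1 − 0.2024) = 13.8.

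For the early case the plain median solves 2^(−t/12) × (16−t)/12 = 0.5. At t = 7 the left side is 0.667 × 0.75 = 0.50, so the median is about 7.0. In the mature case nobody is censored before month 22, so the underlying median of the observed times is the true 12.

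**Step 4: simulation, 4,000 replicates, 13 responders, months.** Means and plain medians are averages over replicates. The Kaplan-Meier median is the median over replicates, with the percentage not reached (NR) in brackets.

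| Follow-up | True median / mean | Censored | Mean, censored taken as complete | Median, censored taken as complete | Mean, events only | Kaplan-Meier median (NR) |
|---|---|---|---|---|---|---|
| 6-18 | 6 / 8.7 | 34% | 5.7 | 5.2 | 4.2 | 6.1 (5%) |
| 6-18 | 12 / 17.3 | 57% | 7.4 | 7.1 | 4.8 | 12.5 (41%) |
| 6-18 | 18 / 26.0 | 68% | 8.2 | 8.0 | 5.1 | not reached (67%) |
| 6-18 | 24 / 34.6 | 75% | 8.6 | 8.4 | 5.2 | not reached (80%) |
| 24-36 | 6 / 8.7 | 4% | 8.3 | 6.3 | 7.4 | 6.0 (0%) |
| 24-36 | 12 / 17.3 | 20% | 13.7 | 12.5 | 10.3 | 11.9 (1%) |
| 24-36 | 18 / 26.0 | 34% | 17.0 | 17.6 | 11.5 | 17.9 (10%) |
| 24-36 | 24 / 34.6 | 44% | 19.1 | 20.9 | 12.3 | 24.0 (27%) |

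With 16 responders the means and plain medians are almost the same. The SD is affected too: at true median 12 the average SD with censoring times taken as complete is 4.0 (early) and 9.7 (mature), against 17.3 for the exponential.

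**Step 5: is the direction general?** Observed time never exceeds true duration, so taking censoring times as complete lowers the mean whenever anyone is censored. Dropping ongoing responders keeps preferentially those with short responses, so with independent censoring it also lowers the mean. The median moves only if censoring falls before the true median.

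**The case against.** The best reply is that the SAP names neither mean nor SD for DoR. SAP 4.1 has its own rule for time-to-event data, with no mean or SD, and DoR is handled as such data in SAP Table 3. The table shells, which would show what is displayed, are separate documents (SAP 8.3). This stands as a caution: the reading in step 1 is an inference, although the phrase would add nothing if it only repeated the Kaplan-Meier rule.

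A reader might go further and infer that the SAP instructs the analyst to treat censored durations as complete, so that two conflicting medians are certain to appear. The documents do not support that. Censoring times are assigned to the range only, which is a common reporting convention, and nothing is said about the other statistics. Nor is the plain median always wrong: in the mature case it is 12.5 against a true 12, and 17.6 against 18.

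Follow-up of at least 2 years is also a fair reply for the median, but only in part. After end of treatment the Schedule of Assessments has no scans, and Protocol 11.2.8 provides quarterly telephone or email contact for survival. A responder who stops treatment without progression may therefore be censored for DoR well before 2 years. SAP Table 3 also censors at new anticancer therapy and after two or more missed assessments.

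Finally, there is no formal hypothesis test, no decision rule uses DoR, and the responder listing lets a careful reader see who is censored. This limits the consequence but does not make the extra summary valid.

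**Conclusion.** The point holds as a fault in a supplementary summary. The Kaplan-Meier analysis of DoR is correctly planned and agrees with Protocol Table 13. The added statistics are undefined for censored responders, and on their most natural reading they include a mean that is biased low under either simple handling.

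The size depends on follow-up. At an assumed true median of 12 months and true mean of 17.3, taking censoring times as complete gives a mean of 7.4 at 6-18 months and 13.7 at 24-36 months; dropping ongoing responders gives 4.8 and 10.3. The plain median is 7.1 in the early case and essentially right at 12.5 in the mature one. It falls clearly short with mature follow-up only at the longest assumed duration (20.9 against 24). These figures rest on exponential durations, independent uniform censoring and response at about 2 months, none of which the documents state. The direction for the mean, under either handling, needs only some censoring and, if responders are dropped, independence of censoring and duration.

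**What to change.** In the first sentence of SAP 5.4.4, strike the words from *summarized* through *also be*. The sentence then says that DoR is analyzed by Kaplan-Meier in confirmed responders only. Report quartiles with 95% confidence intervals, as 5.4.4 already plans, and the time point probabilities that SAP 4.1 already requires for time-to-event data. Add the number of responders still in response. Keep the observed range, with censored values marked by a plus sign.

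The cost is one change of wording and one block fewer in the DoR table. No valid information is lost, and the SAP returns to the protocol's method, so no entry in SAP Section 6 is needed.
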